Protocol Overview/Synopsis	
Patient Population Adults ≥ 18 years with type 1 diabetes or type 2 diabetes using insulin therapy will be enrolled. Although the primary focus of the study is to enroll non-CGM users, CGM users whose glycemic control is suboptimal can be enrolled. Potential participants may be recruited through insurance providers, primary care networks, or health care providers.
 
Baseline Data Collection Baseline data collected will include demographics, height and weight, socioeconomic status, diabetes history, knowledge of and experience with diabetes devices, medical history and medications, and health-related physical activity. Questionnaires will collect information related to hypoglycemia awareness, treatment satisfaction, and psychosocial issues. Participant contact information will be collected. Contact information for the participant's diabetes healthcare provider will also be collected.
 
HbA1c Participant will receive fingerstick HbA1c kits that will be sent to a central lab for measurement after enrollment and at 13 weeks, 26 weeks, 39 weeks, and 52 weeks.
 
Contact between Study Team and Participant Each participant will be assigned to work with virtual clinic team members. Mental health service support options for diabetes-related mental health issues will be discussed as needed.
 
Virtual clinic team members will check in with participants during the initial six months of study follow up to review CGM data and recommendations related to diabetes management. Participants who continue in the optional extended follow-up phase after the first six months can contact the virtual clinic as needed.
 
CGM Use Participants who do not currently use a CGM will use a blinded CGM device for a single sensor wear period prior to CGM initiation. Participants may be asked to use a blinded CGM for an additional sensor wear period(s) if enough CGM data are not available to establish a baseline that can be used as baseline comparator data. Current CGM users will be asked to share their CGM data to confirm that they meet study eligibility criteria and to establish a baseline that can be used as baseline comparator data. Virtual training will include CGM set up, sensor insertion, alerts and alarms, uploading data, and visualizing data.
 
Changes in Insulin Dosing

JAEB CENTER FOR HEALTH RESEARCH

PARTICIPANT AREA	DESCRIPTION

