†††Current CGM users are not required to wear blinded CGM unless current CGM data cannot be shared to establish baseline.

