112 document, with the ethical principles that have their origin in the Declaration of Helsinki, with  
113 the protocol described herein, and with the standards of Good Clinical Practice (GCP).

114 **Chapter 2: Study Enrollment and Baseline Data Collection**

115 **2.1 Participant Recruitment and Informed Consent**

116 Adults (age  $\geq 18$  years) with type 1 diabetes or type 2 diabetes using insulin therapy (Tidepool-  
117 compatible pump or injections) will be enrolled. Although the primary focus of the study is to  
118 enroll non-CGM users, CGM users whose glycemic control is suboptimal can be enrolled.  
119 Participation will be limited to U.S. residents in states where the virtual clinic is licensed; state  
120 eligibility will be verified as part of screening. Potential participants may be recruited through  
121 insurance providers, primary care networks, or health care providers. Potential participants also  
122 may become aware of the study by other means, such as another study participant.

123 Up to 800 individuals may sign the informed consent form to initiate screening. Enrollment will  
124 proceed with the goal of at least 300 participants initiating training for CGM use with the Virtual  
125 Clinic. The goal will be to limit T2D enrollment to no more than 100. Recruitment efforts will be  
126 focused on participants who receive diabetes care in a primary care setting rather than through an  
127 endocrinologist, with a goal of having at least 225 who have not seen an endocrinologist in the  
128 past six months. Eligible participants will be included without regard to gender, race, or  
129 ethnicity.

130 The goal will be to include at least 50 participants  $<25$  years of age and at least 50 participants  
131  $>65$  years of age.

132 **2.1.1 Informed Consent and Authorization Procedures**

133 Individuals who indicate that they are interested will be directed to a website with information  
134 about the study. Interested individuals will be able to communicate with study staff who can  
135 answer questions about the study as part of the informed consent process. Individuals who want  
136 to participate in the study will sign the Institutional Review Board (IRB) approved electronic  
137 consent form. As part of the informed consent process, each participant will be asked to sign an  
138 authorization for release of personal information. Participants will be asked to sign an addendum  

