173 9. Participation in a different diabetes management study during the study  
174 10. Planned relocation to a state other than current state of residence during the study if virtual  
175 clinic is not licensed in the new state.

176 *Individuals working routinely in a state other than current state of residence in the next six  
177 months are also ineligible if the virtual clinic is not licensed in that state.*

178 **2.4 Screening Procedures**

179 Participants will be asked to confirm eligibility by completing a screening questionnaire.  
180 Participants who pass screening will be asked to provide baseline data. Current CGM users will  
181 also be asked to share their CGM data to confirm eligibility. If current data cannot be shared,  
182 current CGM users will be asked to complete blinded CGM data collection. Non-CGM users  
183 will also be asked to complete blinded CGM data collection. Participants will be asked to submit  
184 a baseline HbA1c sample

185 **2.5 Collection of Baseline Data and Testing**

186 After informed consent is signed, baseline data will be collected, including the following:

187 • Contact information  
188 • Date of birth

189 • Demographics  
190 • Height and weight  
191 • Socio-economic information such as education, income, and insurance  
192 • Name and contact information of healthcare provider for diabetes management  
193 • Diabetes history, including diabetes duration, prior management, insulin delivery method,  
194 meal bolus determination method, prior severe hypoglycemia (SH), prior diabetic  
195 ketoacidosis (DKA)  
196 • Medical history  
197 • Medications, including but not limited to medications other than insulin being used for  
198 glycemic control  
199 • Prior CGM experience and knowledge, including why CGM is not used  
200 • General health  
201 • Questionnaires (see Chapter 4)  
202 • Finger stick to measure HbA1c  
203 • Blinded CGM Data Collection

204 **2.5.1 HbA1c**

205 HbA1c will be measured at a central laboratory. The participant will be sent a kit, which will  
206 include a blood collection tube and shipping materials, to obtain a finger stick blood sample. The  
207 sample will be returned to the lab in a prepaid mailer. Participants will be able to view their  
208 HbA1c results through the study website.

209 **2.6 CGM System**

210 Participants will use the Dexcom G6, which is a commercially available CGM system. CGM  
211 data will be shared with CDCES and study team members.

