212 Other sensors that become FDA approved during the course of the study may be included as an  
213 option for participants. If additional sensors are included, the participants will be given  
214 information about CGM system options and will review the CGM systems with a study team  
215 member. A recommendation may be provided for one of the systems based on discussion with  
216 the participant, or there may be an indication that there is no specific recommendation.  
217 Participants will be able to select the CGM system that they prefer, regardless of  
218 recommendation. After a CGM system is selected, the participant may be asked why that system  
219 was selected.

220 **2.7 Blinded CGM**

221 Non-CGM users will use a blinded CGM device for a single sensor wear period (usually at least  
222 10 days) prior to CGM initiation. Current CGM users will be asked to use a blinded CGM device  
223 for a single sensor wear period if their current CGM data cannot be successfully shared to  
224 confirm eligibility. Study supplies required for blinded CGM data collection will be sent to the  
225 participant by mail. An Android phone may be provided which is used as a receiver to collect  
226 data from the blinded Dexcom G6 Pro. Current non-Dexcom CGM users, including pump users  
227 with integrated CGM should continue to use their personal CGM for glucose management.

228 A virtual clinic team member will be available to answer questions about blinded CGM use. The  
229 participants will not be able to see the glucose values and will be expected to follow their normal  
230 diabetes management practice during this blinded CGM use period. The goal will be to obtain  
231 ten days of blinded data. Participants may be asked to use a blinded CGM for an additional  
232 sensor wear period if enough CGM data are not available to establish baseline comparator data.  
233 Participants will be dropped from the study if blinded data cannot be obtained. Participants who  
234 have a serious skin reaction to the sensor during blinded CGM wear that precludes continued use  
235 of a sensor will be dropped. If additional FDA-approved CGM options are available for use in  
236 this study, the participant may be offered the opportunity to try the other CGM system; in this  
237 case blinded data collection would be repeated with another system.

238 **2.8 Psychosocial Screening Questionnaires**

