- 59 • HbA1c, questionnaires, insulin, and other analyses will include all subjects with any
 60 amount of corresponding data following CGM initiation.
- 61 • The tabulations of the safety outcomes will include all participants who enrolled,
 62 regardless of how much data is available.

63 **7 Analysis of Study Endpoints**

64 **7.1 Calculation of CGM Metrics**

65 **7.1.1 Calculation of 13 Week CGM Metrics**

66 All CGM metrics listed in Section 5 will be calculated on a 13-week period for each subject
 67 level. The windows for the 13-week periods are defined as follows:

Time Point	Window
1-13 Weeks	0 to 91 days after the CGM initiation date
14-26 Weeks	92 to 183 days after the CGM initiation date
27-39 Weeks	184 to 274 days after the CGM initiation date
40-52 Weeks	275 to 365 days after the CGM initiation date

68
 69 For each 13-week period, CGM metrics will be calculated by pooling all CGM readings
 70 occurring from 12:00 AM on the first day of the 13-week period up until 11:59PM on the last
 71 day of the 13-week period. For the first 13-week period, the first CGM reading will be the start
 72 datetime of the period. If a participant discontinues CGM prior to the last day of the 13-week
 73 period, then CGM data will include readings up to the last CGM reading on the discontinuation
 74 date. Calibrations will be excluded from all these calculations. CGM metrics for 13-week periods
 75 with less than 168 hours of CGM data will be set to missing.

76 Baseline CGM metrics will be calculated by pooling all blinded CGM readings up to 90 days
77 prior to the date of CGM initiation for each subject. Baseline CGM metrics with less than 72
78 hours of CGM data will be set to missing.

79 The amount of time using the CGM will be calculated as the number of CGM values multiplied
80 by the expected CGM measurement frequency (i.e., 5min in general), with the exception that
81 there can only be one value within the CGM measurement frequency. Percentage of time CGM
82 is used will be calculated as the amount of time using the CGM divided by the total possible time
83 the participant could have used the CGM during the same period. Note that this denominator
84 includes sensor warm-up periods with no CGM values, so this metric will serve as a conservative
85 estimate of CGM use.

86 **7.1.2 Calculation of 4 Week CGM Metrics**

87 All CGM metrics listed in Section 5 also will be calculated on a 4-week interval for each subject.

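### The SAP builds the CGM baseline from blinded readings only, so current CGM users who share their own data, as the protocol provides, have no CGM baseline

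*SAP*

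**What the plan says.** **SAP.** Section 7.1.1 gives one rule for the CGM baseline: "Baseline CGM metrics will be calculated by pooling all blinded CGM readings up to 90 days" before the CGM initiation date. A minimum follows: "Baseline CGM metrics with less than 72" hours of data are set to missing. No rule admits shared, unblinded readings. This fits the population the SAP describes. Its title block names protocol version 2.0 as its basis. Its Table 1 excludes anyone with real-time CGM use in the previous 12 months, describes participants as non-users, and has all of them wear a blinded sensor.

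**Protocol.** The population is wider. Section 2.1 says that, although the focus is to "enroll non-CGM users, CGM users whose glycemic control is suboptimal can be enrolled". The Protocol Summary, under CGM Use, says: "Current CGM users will be asked to share their CGM data to confirm that they meet study eligibility criteria and to establish a baseline" for comparison. The footnote to the Schedule of Study Visits is explicit: "Current CGM users are not required to wear blinded CGM unless current CGM data cannot be shared to establish baseline". Sections 2.4 and 2.7 agree: a current user wears a blinded sensor only if sharing fails.

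**How the baseline is used.** SAP Section 3 makes change from baseline the main test, primarily for CGM metrics, HbA1c and questionnaires. Section 7.4 tests it with a linear mixed model with a random subject effect. Section 7.6 adds complete-case paired tests. Section 7.3 rules out imputation and relies on direct likelihood. Section 6.1 defines the glycemic cohort as all initiators with at least 168 hours of CGM data.

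**The concern.** The protocol collects a CGM baseline from current users for use as comparator data, and the SAP as written discards it. The study has no control arm, so change from baseline carries the efficacy message for the CGM metrics.

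The SAP's cohort includes current users, but its change estimate would come mostly or wholly from non-users. Current users already have CGM, so their gain could well differ. Direct likelihood does not repair this: whether the baseline is missing is determined by prior CGM use, which is not listed as a model term.

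**Working it through.** **Does the baseline become missing?** The documents settle this.

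- Current user who shares data: 0 blinded hours, and 0 < 72, so the baseline is missing.
- Current user who cannot share and wears a blinded sensor: the goal in Protocol 2.7 is ten days, 10 × 24 = 240 hours, and 240 > 72, so the baseline is kept.
- Non-user: blinded wear, so the baseline is kept.

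There is no planned figure to reproduce, because the 300 is a convenience sample.

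**What happens in each analysis?**

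- Paired test (SAP 7.6): users without a baseline drop out.
- Mixed model (SAP 7.4) with baseline as one of the repeated outcomes: they add follow-up values only.
- Mixed model with change as the response: they drop out, as in the paired test. Section 7.4 does not say which form is meant.
- Subgroups (SAP 12): the same model, so the same effect.

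**How large could the error be?** The documents give no share of current users and no expected gains. The following are assumptions, for scale only:

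- p, the share of current users who share data: 5%, 10% or 30% of 300 (15, 30 or 90 people)
- non-users' time in range (TIR): from 45% to 57%, a gain of 12 points
- users' gain g: 3, 8 or 12 points
- SD 15; within-subject correlation ρ 0.5 or 0.7
- either one joint model over the four follow-ups or one model per time point

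Let d be the user minus non-user follow-up mean. In a random-intercept model with users' baseline missing:

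- true all-initiator change = 12 + p(g − 12)
- mixed-model estimate = 12 + p·d·w, with w = (1 − ρ)/(1 + 3ρ) for the joint model and w = 1 − ρ per time point
- paired-test estimate = 12, so its overstatement is p(12 − g)

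The values of w are 0.5/2.5 = 0.20 and 0.3/3.1 = 0.097 (joint), and 0.50 and 0.30 (per time point).

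Example with p = 0.10, g = 3 and equal baselines, so d = −9. The true change is 12 − 0.9 = 11.1. The largest w gives 12 − 0.1 × 9 × 0.50 = 11.55, an overstatement of 0.45. The smallest gives 12 − 0.1 × 9 × 0.097 = 11.91, an overstatement of 0.81. Maximising the expected likelihood with the variances also estimated gives 0.46 to 0.82. The table uses that method.

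Overstatement of the all-initiator TIR change, in points, with equal baselines:

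| Users' gain | Analysis | p = 5% | p = 10% | p = 30% |
|---|---|---|---|---|
| 3 | mixed model | 0.23–0.41 | 0.46–0.82 | 1.39–2.46 |
| 3 | paired test | 0.45 | 0.90 | 2.70 |
| 8 | mixed model | 0.10–0.18 | 0.20–0.36 | 0.60–1.09 |
| 8 | paired test | 0.20 | 0.40 | 1.20 |
| 12 | either | 0 | 0 | 0 |

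**Unequal baselines.** If users start 5 points lower or higher than non-users, the mixed-model error at p = 10% is 0.22 to 0.86 (g = 3), −0.04 to 0.45 (g = 8) and −0.25 to 0.25 (g = 12). The direction is therefore not certain.

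**Within diabetes type.** Results are stratified by type, and Protocol 2.1 says "The goal will be to limit T2D enrollment to no more than 100". With 100 T2D and 200 T1D participants, and all users having T1D, the shares in that stratum would be 15/200 = 7.5%, 30/200 = 15% and 90/200 = 45%. The error grows about 1.5-fold: at 15% with g = 3 it is 0.69 to 1.23 points.

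**The case against.** **Other text seems to cover everyone.** Protocol 2.5 lists blinded CGM collection as a general baseline item, and a schedule footnote ties CGM supplies to completing it. The specific rules in 2.4, 2.7 and the schedule footnote on current users exempt those who share, so this does not cure the mismatch.

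**It is version lag, not a choice.** That is so: for the population in the SAP's Table 1 the blinded-only rule is correct. This explains the cause and makes the fix easy, but the rule remains wrong for the population the protocol now enrols.

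**The effect is probably small.** This largely stands. Non-users are the protocol's primary focus. Read literally, exclusion 2 in Protocol 2.3 admits only current users with TIR below 60% and also more than 1.0% of time below 54 mg/dL, which could be a narrow group. At 5% to 10% users the mixed-model error stays below 0.9 points against an assumed gain of 12. The 30% case is an outer scenario with no support in the documents.

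**All analyses are exploratory.** True, there is no primary outcome, and unlisted analyses are allowed. That still leaves the source, window and minimum hours of these baselines to be chosen after the data are seen.

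**Adding shared data brings its own bias.** This stands as a caution. Shared data also serve to confirm eligibility, so users' later improvement may partly be regression to the mean. As an illustration, assume SD 15, ρ 0.5 to 0.7, and a mean TIR of 45 to 55 before a screen at TIR below 60. Truncation lowers the selected mean by 4.3 to 9.0 points, and a fraction 1 − ρ of that returns: 1.3 to 4.5 points in users, or 0.1 to 0.45 overall at 10% users. This argues for showing users separately, not for leaving their baseline missing. Sensors with another recording interval are largely covered by SAP 7.1.1, which works from the expected measurement frequency.

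**Conclusion.** The concern holds. Under the SAP as written, every current CGM user who shares data has a missing CGM baseline, although the protocol collects one. Confidence in the text mismatch is high. The size is illustrative and depends on the assumed user share, gains, baselines and correlation: from zero, or slightly negative, up to about 0.9 points of TIR at 10% users, and more at larger shares or within the T1D stratum.

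Post-initiation summaries, CGM use, discontinuation, HbA1c and questionnaires are not affected. The point should be fixed. It is not critical, because the analyses are exploratory and the group may be small.

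**What to change.** 1. **Synchronise the SAP and add a baseline rule.** Update the population, eligibility and CGM-use text in SAP Table 1 to the current protocol, and add to 7.1.1, for example: *For current CGM users, baseline metrics are calculated from shared CGM readings in the last 14 days available within the 90 days before the CGM initiation date or, if data cannot be shared, from blinded readings. The 72-hour minimum applies to both.* The 14 days is only an example, close to the blinded period (about two weeks in the schedule, a ten-day goal in Protocol 2.7); any window stated in advance would do. State that for existing users the CGM initiation date is Training 1 (Day 0), as in the schedule.
2. **Optional, for interpretation.** Add baseline CGM use (yes/no) to SAP Section 12 and report change by it next to the overall result for CGM metrics, HbA1c and the questionnaires that receive change tests. The three screening questionnaires have summary statistics only. The pooled HbA1c change is a valid cohort mean and needs no correction. Skip this step if the separate table shells, not available here, already do it.
3. **Add a caution.** Note that shared data also confirmed eligibility, so part of users' change may be regression to the mean.

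The cost is one SAP amendment using data the protocol already collects, and Protocol 6.1 requires the SAP to be final only before the study is completed. The optional split adds a stratum that may be very small.

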108 used to screen for depression. Each item is scored on a scale of 0 to 3, with a higher value
109 denoting more depressive symptoms. The total score is calculated by summing the
110 individual responses to each question. Per the scoring instructions, total scores are set to
111 missing for participants who skip more than one question. A total score of ≥ 10 denotes
112 major depression, and a score of ≥ 20 denotes severe major depression.
- 113 • Diabetes Distress Scale Management Distress Subscale: This questionnaire consists of
114 questions about the participant's distress regarding diabetes management. Items are
115 ranked on a scale of 1 to 6, where a 1 denotes that the item is not a problem at all and a 6
116 denotes that it is a very serious problem. For this questionnaire, a mean score will be
117 calculated across all questions.
- 118 • Hypoglycemia Fear Survey Worry Subscale: This questionnaire consists of items asking
119 the participant about his or her worries regarding what may occur as a result of low blood
120 sugar. Items are scored on a scale of 0 to 4. Higher numbers denote responses that are
121 more worrisome. The total score is calculated by summing the responses to each
122 question.
- 123 • CDC Healthy Days: This is a questionnaire about the participant's general mental and
124 physical health. It estimates the number of days that the participant's mental and physical
125 health has been adequate over the past month, in addition to the impact that the
126 participant's health has had on his or her daily life. Analyses will report the percentage of
127 participants ranking their general health as either fair or poor. Additionally, the number
128 of unhealthy days over the past 30 days will be calculated by summing the number of
129 reported unhealthy mental and physical days. The sum will be truncated at 30 days if it
130 exceeds 30.
- 131 • Hypoglycemia Confidence Survey: This questionnaire asks the participant about their
132 level of confidence regarding the avoidance of problems with daily activities due to
133 hypoglycemia. Items are ranked on a scale of 1 to 4, with higher numbers denoting a
134 higher level of confidence. For this questionnaire, a mean score will be calculated across
135 questions.
- 136 • Diabetes Technology Attitudes Survey: This questionnaire consists of 5 questions about
137 diabetes technology. Responses to each question are ranked on a scale of 1 to 5. Higher
138 numbers denote more satisfaction with diabetes technology. A total score is calculated as
139 the sum of the individual responses to each question.
- 140 • Glucose Monitoring Satisfaction Survey: This questionnaire asks the participant to
141 provide a response on a scale of 1 to 5 to several questions about their satisfaction with
142 their current glucose monitor. The directionality of the responses varies across questions,
143 so some questions are reverse scored in the calculation of scores. The questionnaire
144 includes four subscales, and the overall score is tabulated as a mean across all questions
145 for the full questionnaire and each subscale.

- Sleep Quality Scale: This questionnaire consists of a single item asking the participant to rank their sleep quality on a scale of 0 to 10, with a higher number denoting better sleep. For this questionnaire, a mean score will be calculated across questions.
- Benefit of CGM Survey: This questionnaire asks the participants questions about things that are good about wearing a CGM. The participants are asked to rank their agreement with each statement on a scale of 1 to 5. A higher number indicates more agreement, which would imply more satisfaction with using a CGM. For this questionnaire, a mean score will be calculated across questions.
- Barriers of CGM Survey: This questionnaire asks the participants questions about things that are bad about wearing a CGM. The participants are asked to rank their agreement with each statement on a scale of 1 to 5. A higher number indicates more agreement, which would imply less satisfaction with using a CGM. For this questionnaire, a mean score will be calculated across questions.
- CGM Discontinuation Survey (only administered to subjects who discontinue CGM): This questionnaire asks the participants several questions about why they discontinued CGM. For this survey, only responses to each individual question will be tabulated.

The electronic data capture system for this study will allow the subjects to skip questions on the questionnaires. For all questionnaires, at least 75% of questions must be answered in order to be included in the analyses (unless specified otherwise above). The 75% rule described above will be applied separately for the mean score and each subscale so it is possible that the sample size will be different for some subscales. The score used for the analyses will only be based on the questions that were answered. Analyses will be limited to subjects who are included in the primary cohort (no imputation).

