The goal for the study is to include at least 300 participants who initiate CGM. This is a convenience sample and not based on statistical principles.

5 Outcome Measures

The following quantitative study outcome measures will be tabulated by diabetes type using summary statistics appropriate to the distribution:

- HbA1c
- Percentage of time using the CGM
- Hours of CGM use
- Mean of sensor glucose levels
- Percentage of time spent with sensor glucose levels <54 and <70 mg/dL
- Percentage of time spent with sensor glucose levels >180 and >250 mg/dL
- Percentage of time spent with sensor glucose levels in the target range (70-180 mg/dL)
- Glycemic variability measured by the coefficient of variation
- Total daily insulin (units/kg)
- Total daily basal insulin (units/kg)
- Total daily bolus insulin (units/kg)
- Patient Health Questionnaire-8
- Diabetes Distress Scale Management Distress Subscale
- Hypoglycemia Fear Survey Worry Subscale
- CDC Healthy Days
- Hypoglycemia Confidence Survey
- Diabetes Technology Attitudes Survey
- Glucose Monitoring Satisfaction Survey
 - Openness Subscale
 - Emotional Burden Subscale
 - Behavioral Burden Subscale
 - Trust Subscale
- Sleep Quality Scale
- Benefits and Barriers of CGM Survey
- Percentage of CGM discontinuations
- CGM Discontinuation Survey (only administered to subjects who discontinue CGM)
- Positive screen for mental health

41 ○ Positive screen triggered by Patient Health Questionnaire-8
 42 ○ Positive screen triggered by Diabetes Distress Scale
 43 ○ Positive screen triggered by Hypoglycemic Fear Survey Worry Scale
 44 • Behavioral health service utilization
 45 • Behavioral health metrics
 46 • Cost of care over time
 47 • Service utilization such as hospitalizations, ER visits, prescriptions filled

48
 49 CGM, HbA1c, and insulin outcomes will be evaluated at baseline and 13, 26, 39, and 52 weeks.
 50 CGM and insulin outcomes will also be evaluated over the first 26 weeks and last 26 weeks.
 51 Questionnaires will be evaluated at all time points they are collected.

52 **6 Description of Statistical Methods**

53 **6.1 Analysis Cohorts**

- 54 • All subjects enrolled in the study who initiate the CGM and have at least 168 hours of
 55 CGM data will be included in the tabulations of demographics and the glycemic
 56 outcome measures listed in Section 5
- 57 • CGM use assessment will include all subjects who stayed in the study at least one week
 58 following CGM initiation.

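### Three questionnaires are scored as sums over answered items only, so as written a permitted skipped item adds 0: always too low for Technology Attitudes, possibly too low for PHQ-8 and Hypoglycemia Worry

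*SAP*

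**What the plan says.** SAP 7.2 defines three totals as sums of item ratings.

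- PHQ-8: eight items rated 0 to 3, summed, with cuts at 10 and 20 applied to the total. Citing scoring instructions that it does not reproduce, the SAP sets the total to "missing for participants who skip more than one question".
- Hypoglycemia Worry: items rated 0 to 4. "The total score is calculated by summing the responses to each" question.
- Technology Attitudes: five items rated 1 to 5. The total is "the sum of the individual responses to each question".

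The closing paragraph of 7.2 says that the data capture system "will allow the subjects to skip questions on the questionnaires". It requires 75% of items to be answered unless an instrument has its own rule, and then states: "The score used for the analyses will only be based on the questions that were answered". The same paragraph and Section 7.3 rule out imputation. Sections 7.2 to 7.4 contain no proration rule.

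Other text points to means. Section 7.4 summarises questionnaires by mean scores, and Section 14 names a mean score for both Worry and Technology Attitudes. Section 7.4 limits PHQ-8, Diabetes Distress and Worry to summary statistics, and fits the change-from-baseline mixed model to the other questionnaires at 26 and 52 weeks.

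**The concern.** Scoring only the answered items is harmless for a mean, because the divisor shrinks with the numerator. A sum has no divisor, so leaving an item out is arithmetically the same as scoring it 0. On Technology Attitudes, 0 is not a possible answer.

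Two things are at stake. First, Technology Attitudes is tested for change from baseline. If the share of forms with a skip differs between baseline and follow-up, part of the estimated change is a scoring artefact. Direct likelihood does not help, because the understated total enters as an observed value. Second, the PHQ-8 total is compared with fixed cuts, so losing even one point can change a participant's class.

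**Working it through.** **Inputs.** Item ranges, the PHQ-8 and Technology Attitudes item counts, the 75% rule and the PHQ-8 skip limit come from SAP 7.2. The Worry count (6) comes from the table in Protocol Chapter 4, because the SAP does not give it. The SAP states that it is based on Protocol Version 2.0, and its exclusion of prior CGM users differs from the protocol supplied, so that count may come from a different protocol version.

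**Skips admitted.** With k items, the minimum answered is m = ceil(0.75 × k); for PHQ-8 it is k − 1.

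| Instrument | k | m | Skips admitted | Full range | Range with one skip, as written |
|---|---|---|---|---|---|
| PHQ-8 | 8 | 7 | 1 | 0–24 | 0–21 |
| Worry | 6 | ceil(4.5) = 5 | 1 | 0–24 | 0–20 |
| Technology Attitudes | 5 | ceil(3.75) = 4 | 1 | 5–25 | 4–20 |

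**Loss per form.** Let S be the answered sum and x the unseen answer. The full total is S + x and the score as written is S, so the loss is x.

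- Technology Attitudes: x is 1 to 5, so a loss is certain. A participant who would answer 4 throughout scores 4 × 4 = 16 instead of 20.
- PHQ-8: x is 0 to 3. Worry: x is 0 to 4. There is no loss if x = 0.
- If x equals the person's mean on the other items, the relative loss is 1/k: 12.5% for PHQ-8, 16.7% for Worry and 20% for Technology Attitudes.

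**PHQ-8 cuts with one skip.** The prorated value is S × 8/7.

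| S | Possible full total | Prorated | Cut in question |
|---|---|---|---|
| 7 | 7–10 | 8.0 | 10 |
| 8 | 8–11 | 9.1 | 10 |
| 9 | 9–12 | 10.3 | 10 |
| 17 | 17–20 | 19.4 | 20 |
| 18 | 18–21 | 20.6 | 20 |
| 19 | 19–22 | 21.7 | 20 |

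All six sums could belong to someone whose full total reaches the cut. Proration moves three of them (9, 18 and 19) across it.

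**Group mean.** If a share q of forms has one skip and the skipped answers average a, the mean shifts by −q × a. The documents give neither value. Assuming q = 2% to 10% and a = 4 for Technology Attitudes, the shift is −0.02 × 4 = −0.08 to −0.10 × 4 = −0.40 points on a 5–25 scale.

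**Change from baseline.** With the same a at both times, the artefact is −a × (q at follow-up − q at baseline). It is zero if the shares are equal. For 2% at baseline and 10% at follow-up it is −4 × 0.08 = −0.32 points.

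**The case against.** The strongest reply is that scoring a skip as 0 is inferred from the text and never stated. Sections 7.4 and 14 speak of mean scores, and Section 14 does so by name for Worry and Technology Attitudes. If the programs take means of answered items, no skip is scored 0. This stands as a reason to reconcile the sections, but it does not remove the problem: the section that defines the scores says sum, and two programmers could score the same form differently.

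Three stronger readings are tempting, and the documents do not support them.

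- A reader might infer that a skip lowers the score on all three instruments. That is certain only for Technology Attitudes.
- A reader might infer biased change tests for all three. Section 7.4 gives PHQ-8 and Worry summary statistics only.
- A reader might take an answered PHQ-8 sum of 9 as a proven misclassification. The full total lies between 9 and 12; if the unseen answer is 0, the class below 10 is correct. The value 10.3 is an estimate.

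Two further points stand. Proration assigns the skipped item the person's own mean, which is a form of imputation and conflicts with 7.2 and 7.3 as worded. It makes the same assumption that the SAP already accepts when it averages answered items on its mean-scored surveys. Also, the PHQ-8 scoring instructions cited in the SAP may already cover a single skip, which cannot be checked here.

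**Conclusion.** The concern holds as a scoring error in SAP 7.2 as written. For Technology Attitudes the error is certain whenever an item is skipped (1 to 5 points, with an impossible total of 4 allowed), and it reaches a tested outcome. For PHQ-8 and Worry it is conditional on a nonzero unseen answer and affects descriptive results only, including the PHQ-8 classes at 10 and 20. Positive mental health screens are listed outcomes in SAP Section 5, but their thresholds are not stated, so no effect on them can be claimed.

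The effect is probably small: at most one item per form is involved, the SAP calls all analyses exploratory, and it names no primary outcome. The group shift of 0.08 to 0.40 points for Technology Attitudes rests wholly on the assumed skip share and mean answer. The limit of one skip on Worry rests on the protocol's count of six items. The case for acting is that the score can only be understated, never overstated, and the correction is cheap.

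**What to change.** 1. In SAP 7.2, define the total for PHQ-8, Worry and Technology Attitudes as (mean of answered items) × (number of items) whenever the minimum-answer rule is met. First check the PHQ-8 scoring instructions that the SAP cites. One-skip multipliers are 8/7, 6/5 and 5/4; the Technology Attitudes example of 16 returns to 16 × 5/4 = 20. Leave the rule for mean-scored surveys as it is.
2. State in 7.2 and 7.3 that this within-form proration is an exception to the no-imputation rule.
3. Reconcile the sums in 7.2 with the mean scores in 7.4 and Section 14. After proration the total is a fixed multiple of the mean, so the Spearman correlations in Section 14 are the same under either label.
4. Give the Worry item count in the SAP.

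The cost is a few sentences in the SAP and about one line of code per instrument. No data collection changes. Reporting the number of forms with a skip by time point would show whether the issue mattered.
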